13.1 Language for data recording

The PME will be conducted in English. The prover will be requested to fill in the prover's day book proforma Form E in English/ any other language, as preferred. In case the symptoms have been recorded in other language apart from English, then in that case the investigator should translate the symptoms to English while elaborating them in Symptom elaboration sheet (Form F). The proving symptoms will be compiled in English.

13.2 Definition of proving symptom^[9]

Proving Symptoms are any change in normal objective and/or subjective state of mind or body as experienced by the prover, or as observed by proving investigator and/or others occurring during proving period, which are possibly related to the IPS. They are those symptoms or signs that are recorded during the Proving period where causality by the IPS is possible. Symptoms that occur in a severity, duration and frequency consistent with historical tendency (i.e. Unchanged (U) symptoms) of a subject should not be reported as Proving symptoms. Likewise, care should be taken to exclude from this category any symptoms related to a cause that can confidently be determined to be external to the Proving. Proving symptoms will include:

- New symptoms, not previously experienced (NS)
- Unexpected change representing worsening or aggravation of ongoing or recurring symptoms (C-)
- Unexpected change representing an improvement of ongoing or recurring symptoms (C+)
- Unexpected recurrence of past symptoms (RS)
- Abnormal values of laboratory parameters that were in the normal range during the PME

Proving symptoms are therefore all changes in clinical events and laboratory findings reported by volunteers during the trial and recorded in the final report. These are the findings claimed by authors to be compared by practitioners with the symptoms of their patients in order to prescribe the homeopathic medicinal product.

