9.2.1 Eligibility for study

Ages:	18-60 years
Genders:	Both male and female
Health status:	Good state of health both somatically & psychologically

9.2.2 Inclusion Criteria:

- Healthy individuals with no apparent disease and normal routine laboratory parameters during screening
- Healthy individuals identified as fit for proving by experts
- Intelligent enough to record carefully the facts, subjective and objective symptoms generated by the IPS during proving.
- Able to be informed of the nature of the study and willing to give written informed consent

9.2.3 Exclusion Criteria:

- Any disease or condition which might compromise the hematopoietic, renal, endocrine, pulmonary, central nervous system, cardiovascular, immunological, dermatological, gastro-intestinal or any other body system
- Persons with colour blindness.
- Persons who have undergone surgery in last two months.

- Planned medical / dental treatment during the proving period including herbal or dietary supplements, procedures, or medications that are likely to interfere with, or substantially alter, responsiveness to the proving substance.
- Volunteers on regular medication (allopathic, ayurvedic, homoeopathic, naturopathic, unani, etc.) for any acute or chronic disease.
- Participant must not be on any homoeopathic remedy in the preceding one month and have had no significant change in health status in last one month.
- Emotionally disturbed, hysterical or anxious persons.
- Persons having known history of allergies, food hypersensitivity, etc.
- Women during pregnancy, puerperium and while breast-feeding and women who have undergone hysterectomy.
- Smokers who smoke more than 10 cigarettes per day
- Recent history of alcoholism / drug addictions or unlikely to refrain from excessive alcohol consumption / drug intake during the study period
- Participation in another clinical or proving trial during the last 6 months

9.3 Sample size:

Each drug will be proved on a minimum of 30 participants, including 30% control. Adding 20% dropout, minimum volunteers needed to enroll in proving becomes 40. Each centre must enroll minimum 15 to a maximum of 25 volunteers in proving. Efforts are to be taken to include atleast 20% volunteers from non-homoeopathic background.

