9.4.19 Post –Trial (Terminal) Medical examination (Form D)

After all the batches of the study medication are consumed and a subsequent washout period of 30 days, the provers are examined again as in the PME, and the process is called 'Terminal Medical Examination' (TME). The TME must be completed within two weeks after completion of the washout period.

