- G.** Symptoms that involve multiple body parts or organs in a similar manner or multiple symptoms within the same subject with a similar associated modality, forming an easily recognizable pattern of reaction
- H.** Similar symptoms occurring in multiple provers. Such symptoms may be related by similar sensation, modality, or body system and can be recognized through a qualitative analysis similar to red – line symptom reporting in homoeopathic literature.
- I.** Any objective finding/including abnormal laboratory values associated with subjective symptoms.

14.1.3 Grading of the Drug Proving Symptoms as per their value:

Symptoms will be graded as follows:

Grade I symptoms:

- Symptoms appearing in more than 2 provers, at two different study sites (Symptom in 1 or more prover at one site and similar symptom in 1 or more provers at the second site. i.e. if two provers separated by distance and time with no contact with each other what so ever give the same symptom).
- Peculiar, rare, queer, strange, characteristic symptoms
- Symptoms reappearing from prior provings.

Grade II symptoms

All proving symptoms other than those in grade I

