9. GENERAL PHYSICAL EXAMINATION

Pallor	Present/absent
Jaundice	Present/absent
Cyanosis	Present/absent
Clubbing	Present/absent
Oedema (general/ partial)	Present/absent
Enlarged Lymph nodes	Present/absent
Tongue (colour/coating, etc)	
Nails (colour of nail bed/specific features, etc)	
Oral health (health of gums & teeth)	
Blood pressure	mmHg

Pulse rate	Per minute
Temperature	Degree F
Respiratory rate	Per minute

Observations- any of the factors which make the participant unfit for proving as per protocol	1
	2
	3
	4
	5
Based upon the findings of History & General Examination, whether the volunteer is suitable or not for enrollment in proving (chose the relevant option)	Suitable for proving Not suitable for proving
Name of the investigator	
Date of examination	
Signature of investigator	
Stamp of investigator	

If the volunteer is Suitable for proving, refer for laboratory investigations as per Form D - Part - II-A.

Part-II-A
To be filled by Pathologist

LABORATORY EXAMINATION

Investigation	Value	Reference range	Date of investigation
BLOOD			
Hb			
TLC			
DLC			
ESR			
Platelet count			
Peripheral smear			
BLOOD SUGAR			
Fasting			
LIPID PROFILE			
Triglyceride			
LDL			
VLDL			
HDL			
Cholesterol			
LIVER FUNCTION TEST			
Bilirubin (Direct)			
Bilirubin (Indirect)			
T. Bilirubin			
SGOT			
SGPT			
Alk. Phosphatase			
Albumin			
Globulin			
A/G ratio			
KIDNEY FUNCTION TEST			
S. creatinine			
S. urea			
Total protein			
URIC ACID			
THYROID PROFILE			
T3			
T4			
TSH			

URINE EXAMINATION

	Investigation	Value	Reference range	Date of investigation
Routine examination				
Microscopic examinations				

STOOL EXAMINATION

	Investigation	Value	Reference range	Date of investigation
Routine examination				
Microscopic examinations				

Observations- any of the factors which make the participant unfit for proving as per protocol	1
	2
	3
	4
	5
Based upon the findings of Laboratory Examination, whether the volunteer is suitable or not for enrollment in proving (chose the relevant option)	Suitable for proving Not suitable for proving
Name of the pathologist	
Date of pathological examination	
Signature of pathologist	
Stamp of pathologist	
Signature of investigator	

Note for site investigator: If the volunteer is Suitable for proving, refer for radiological investigations as per Form D – Part – II-B.

Part-II-B

To be filled by Radiologist

X-Ray chest-

Date of X-Ray:

Findings:

ULTRASOUND WHOLE ABDOMEN

Date of ultrasound:

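### Section 13.2 admits any newly abnormal laboratory value as a proving symptom, with no filter for chance variation, and the scheduled re-test comes too late to be assigned to a batch

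*Protocol*

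**What the plan says.** Protocol section 13.2 defines proving symptoms and lists five kinds. The last is "Abnormal values of laboratory parameters that were in the normal range during the PME". The section ends: "Proving symptoms are therefore all changes in clinical events and laboratory findings reported by volunteers during the trial and recorded in the final report". Its general condition is: "They are those symptoms or signs that are recorded during the Proving period where causality by the IPS is possible".

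Entry under section 9.2.2 requires "Healthy individuals with no apparent disease and normal routine laboratory parameters during screening". The panel is in Form D Part II-A, to which the site investigator sends each suitable volunteer ("refer for laboratory investigations as per Form D - Part - II-A"). Section 9.4.19 says that after all batches and a further 30-day washout "the provers are examined again as in the PME", and that "The TME must be completed within two weeks after completion of the washout period". Sections 9.4.16 and 9.4.17 also allow laboratory tests during a batch when needed, and Form F records these with batch number and date.

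Section 13.4 attaches to each finding the day counted from the start of the batch and the potency of that batch. It separates placebo-batch findings from IPS-batch findings within the verum arm. Section 14.2 then computes two figures with IPS takers as the denominator: the share with at least one proving symptom, and the number of findings per volunteer. Section 14.1.2 item I names as a characterizing feature "Any objective finding/including abnormal laboratory values associated with subjective symptoms".

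**The concern.** Provers are chosen because their values are in range, and a long panel is then measured again months later. Some values will fall out of range whether or not the substance does anything. Section 13.2 has no rule to separate these from an effect.

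Two things are at stake. The section 14.2 figures have no placebo rate set against them, so chance laboratory findings would pass straight into the reported incidence and count. Chance values could also enter the drug picture, which section 13.2 says practitioners will compare with their patients' symptoms. Section 13 itself warns against letting in too much non-specific data.

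**Working it through.** The protocol gives no chance rate for laboratory findings, so there is no figure of its own to reproduce.

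**Number of tests (Form D Part II-A).** Haematology 5 (Hb, TLC, DLC counted once, ESR, platelets) + fasting sugar 1 + lipids 5 + liver 9 + kidney 3 + uric acid 1 + thyroid 3 = 27. Peripheral smear, urine and stool are not counted. Several tests are linked arithmetically (the bilirubin fractions; albumin, globulin, A/G ratio and total protein), so 22 effective tests are also tried.

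**Number of provers (section 9.3).** Minimum 30 with 30% control: 0.70 × 30 = 21 verum, 9 placebo. With 40 enrolled: 0.70 × 40 = 28 verum, 12 placebo.

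**Assumptions, not in the protocol.** Two-sided 95% reference ranges; correlation ρ of 0.7 to 0.9 between a prover's PME and TME values; correlation r of 0 to 0.5 between tests.

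**Step 1: one test.** Let q = P(abnormal at TME given normal at PME), from a bivariate normal with limits ±1.96. This gives q = 0.0352 at ρ = 0.7, 0.0295 at 0.8 and 0.0214 at 0.9.

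**Step 2: whole panel, independent tests.** P(at least one) = 1 − (1 − q)^k.

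| ρ | k = 27 | k = 22 |
|---|---|---|
| 0.7 | 62% | 55% |
| 0.8 | 56% | 48% |
| 0.9 | 44% | 38% |

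**Step 3: correlated tests.** Simulation with equal pairwise correlation r = 0.5, among provers all normal at PME:

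| ρ | k = 27 | k = 22 |
|---|---|---|
| 0.7 | 37% | 33% |
| 0.8 | 32% | 29% |
| 0.9 | 24% | 21% |

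Over steps 2 and 3 the range is 21% to 62%, or about 20-60%. For 21 verum provers: 0.20 × 21 = 4.2 and 0.60 × 21 = 12.6, so about 4 to 13.

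**Step 4: does the placebo-matching rule of section 13.4 remove these?** That rule drops findings identical in location, sensation, modalities and concomitants, which do not describe a laboratory value. Suppose it were applied by parameter instead. The chance that at least one placebo prover shows the same parameter abnormal is 1 − (1 − q)^n. With q = 0.0214 and n = 9 this is 18%; with q = 0.0352 and n = 12 it is 35%. Most chance findings would stay.

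**Step 5: batch attribution.** By TME a verum prover has taken one placebo batch and the IPS batches (section 9.4.9), with at least two potencies (section 9.4.11). One measurement after all of them carries no batch, no day within a batch and no potency. A test ordered during a batch does carry the batch number and date.

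**The case against.** The strongest reply is that section 13.2 never says in terms that TME values count. Its stem requires that the finding arise in the proving period and that the IPS be a possible cause. The proving period is not defined. Section 13.3 compiles PME and TME separately from the batch-wise symptoms. Section 14.2 counts only what could stand as its own repertory subheading. Section 15.1 sends clinically significant end-of-study abnormalities to adverse-event reporting. This stands as real doubt, so a reader should not infer that every out-of-range TME value is a proving symptom by definition. But none of these provisions states a filter for random laboratory variation, and the closing sentence of section 13.2 points towards inclusion.

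The size is also open to challenge. The same model implies that only 0.95^27 = 25% of healthy applicants would be normal on all 27 tests if the tests were independent, and about 52% at r = 0.5. Form D asks the pathologist to judge suitability, so in practice abnormal may mean a clinical judgement, and the chance rate would then be lower. If each test counted in one direction only (2.5% tail, 27 independent tests), the rates would be 37%, 32% and 25% at ρ = 0.7, 0.8 and 0.9.

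Three stronger readings are tempting and are not supported:

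- That no laboratory value can be tied to a batch. This is true only of the scheduled TME panel. TME values can also still be compared between the randomised arms.
- That section 14.1.2 item I contradicts section 13.2. Item I describes symptoms already identified as proving symptoms; it is a narrower tier of the same scheme.
- That the incidence in section 14.2 is inflated by 20-60 percentage points. Many of these provers may already qualify through a subjective symptom, and the overlap cannot be worked out from the protocol.

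**Conclusion.** The point holds as a defect of definition. Section 13.2 admits newly abnormal laboratory values without a threshold, a repeat or a significance rule, and the only scheduled repeat cannot meet the attribution requirements of section 13.4. If TME values are counted, about 20-60% of provers (about 4-13 of 21 on verum) would meet the laboratory item by chance. This rests on 95% reference ranges, test-retest correlation 0.7-0.9, between-test correlation 0-0.5 and 22 to 27 effective tests, and on a bare out-of-range reading of abnormal. It measures how often the laboratory item would be met, not the change in the at-least-one-symptom rate. The plan should be changed, because it leaves open whether these values count and states nothing that would screen them.

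**What to change.** In section 13.2, count a laboratory value as a proving symptom only if it was measured in the intake, observation or washout period of a batch and accompanies a subjective or clinical proving symptom in that same period. The accompanying-symptom condition is close to section 14.1.2 item I; the same-period condition is new. State that values found only at TME are excluded from the section 14.2 incidence and the per-volunteer count. Report PME-to-TME shifts separately by randomised arm, which keeps the comparison that randomisation supports.

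The cost is one reworded definition and one table, with no extra measurements. The downside is that fewer findings are counted, and isolated objective changes with no accompanying symptom will appear only in the shift table.

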13.3 Data compilation

The original source documents i.e. PME, Prover's Day Book Proforma, Symptoms Elaboration Proforma', TME form, case off form, adverse event reporting forms will be sent by investigators from the centres to the coordinators at CCRH headquarters.

Phases of data compilation:

- 1: PME & TME compilation
2. Prover wise entry of symptoms produced(or symptoms not produced) with individual batch
- 3: De-coding & segregation of verum & placebo symptoms
- 4: Analysis & matching of symptoms and compilation of drug pathogenesis

The data base will be prepared by the coordinator at the headquarters. Un-blinding or breaking of the randomization codes will be done by the study PI at the headquarters after the study has been completed at the study site, followed by first & second phase of data compilation.

13.4 Compilation of Proving symptoms

The sign(s) &/or symptom(s) generated in each prover after the end of each drug batch will be noted along with their prover code, name of the proving center, number of doses after which each of the signs or symptoms appeared and the duration for which they persisted. The sign(s) &/or symptom(s) generated in the drug group will be segregated from those of the control group. In the intervention group sign(s) &/or symptom(s) generated during intake of placebo batch will be segregated from those appearing during IP intake. The sign(s) &/or symptom(s) which are identical (exactly the same in terms of location, sensation, modalities, concomitants) in both drug and placebo will not be included as proving symptoms.

These proving symptoms will be identified. These proving symptoms will be compiled and arranged as per the schema of the Kent's Repertory i.e. Mind, Vertigo, Head, Eye, Ear,etc.

To each sign and symptom generated, the following information will be linked:

- Prover code: Number
- Prover gender: M/F
- Proving Center: XX
- Day of symptom appearance (Day 1 being the day of administration of the study medication batch)
- Time of day of symptom occurrence (HH:MM) *(if information available)*
- Characterizing feature(s)
- Duration for which the symptom persisted in terms of hours/days
- Potency of the IPS in the study medication batch

This information would then be the basis where the following types of symptoms are distinguished:

- Characteristic symptoms (if reported)
- Ongoing symptoms that have unexpectedly and markedly improved
- Proving symptoms with one or more characterizing features

14. DATA ANALYSIS

14.1 Qualitative analysis:

14.1.1 Symptom selection criteria:

Drug proving data is in the form of symptoms, where there is no measure of efficacy, but description of individual proving symptoms where qualitative research evaluation will be applied. The evaluation will be done by compilation of the proving symptoms in different categories, representing a certain probability to be associated with the remedy and therefore are the most important ones for further clinical verification.

Example: a symptom will belong to the remedy with great probability if at least one of the following criteria is met^[5].

- Occurrence of the symptom in two or more volunteers
- Objective, measurable signs corroborating with the symptoms
- Distinct intensity of the symptom
- Occurrence of the symptom several times shortly after administration of the drug
- Recurrence of the symptom several times over the course of a number of days
- Recurrence of the symptom using different potencies
- Striking, singular, uncommon symptoms
- Striking, seldom or paradox modalities and/or concomitants of the symptom

However, all symptoms including those appearing in lesser number of provers, less distinct or common symptoms will all be included in the proving data. Symptoms, which are not thought to belong to the drug picture, would also be stated, but under separate headings, marked in a specific manner so they are not lost for clinical verification. Such symptoms may be compared with the clinical verification symptoms at a later stage if required.

14.1.2 Characterizing features of proving symptoms:

All provers are to be included in the analyses. The symptoms obtained under verum or placebo must be listed separately. The proving symptoms are identified and their characterizing feature^[9] will be detailed:

- A.** New symptoms with marked severity, duration or frequency
- B.** Ongoing or recurring symptoms present during the proving that have been unexpectedly and markedly improved
- C.** Ongoing or recurring symptoms that have been unexpectedly and markedly worsened
- D.** Symptoms that recur from the past but have not occurred in the 12 months preceding the proving
- E.** Symptoms that display alteration with another symptom in a single volunteer in such a way that the alteration is strongly individualizing
- F.** Symptoms associated with modalities or concomitant symptoms occurring in other parts of the same prover
- G.** Symptoms that involve multiple body parts or organs in a similar manner or multiple symptoms within the same subject with a similar associated modality, forming an easily recognizable pattern of reaction
- H.** Similar symptoms occurring in multiple provers. Such symptoms may be related by similar sensation, modality, or body system and can be recognized through a qualitative analysis similar to red – line symptom reporting in homoeopathic literature.
- I.** Any objective finding/including abnormal laboratory values associated with subjective symptoms.

14.1.3 Grading of the Drug Proving Symptoms as per their value:

Symptoms will be graded as follows:

Grade I symptoms:

- Symptoms appearing in more than 2 provers, at two different study sites (Symptom in 1 or more prover at one site and similar symptom in 1 or more provers at the second site. i.e. if two provers separated by distance and time with no contact with each other what so ever give the same symptom).
- Peculiar, rare, queer, strange, characteristic symptoms
- Symptoms reappearing from prior provings.

Grade II symptoms

All proving symptoms other than those in grade I

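### Section 14.1.1 attributes a symptom to the remedy on any one of eight criteria, none of which compares drug with placebo, so an inert substance is likely to yield attributed symptoms over a wide range of assumed rates

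*Protocol*

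**What the plan says.** Section 14.1.1 gives the selection rule: "a symptom will belong to the remedy with great probability if at least one of the following criteria is met". The first of the eight criteria is "Occurrence of the symptom in two or more volunteers". Others include "Distinct intensity of the symptom" and "Striking, singular, uncommon symptoms". The rest cover corroborating measurable signs, repetition soon after dosing, recurrence over days, recurrence at other potencies, and unusual modalities or concomitants.

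Section 14.1.3 then grades symptoms. Besides a criterion on agreement between sites, Grade I is given to "Peculiar, rare, queer, strange, characteristic symptoms" and to "Symptoms reappearing from prior provings".

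Placebo enters at three other places:
- Section 13.4 separates symptoms by arm and, in the verum group, by batch. Symptoms that are "exactly the same in terms of location, sensation, modalities, concomitants" "in both drug and placebo will not be included as proving symptoms".
- Section 14.1.2 asks for verum and placebo symptoms to be listed separately.
- Section 14.2 defines two incidence measures, both with IPS takers only as the denominator.

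In section 13.3, decoding is phase 3 and the analysis and matching of symptoms is phase 4.

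**The concern.** The objective in section 7 is to identify the effects of the IPS, and the rule in 14.1.1 is what turns a recorded symptom into such an effect. Intensity, oddness, an odd modality and a corroborating sign describe the symptom. Without a comparison they carry no information on whether the drug caused it, and a healthy person on placebo can report a symptom with any of these features. The criteria are not applied to placebo symptoms, so the trial never learns how often placebo symptoms would pass.

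The exclusion in 13.4 does not fill this gap. It is all or nothing and needs agreement on four attributes, so the more detailed or unusual a description is, the less likely it is to find a placebo match. Those are the descriptions that 14.1.1 and Grade I reward. Since decoding comes before matching, words such as striking and distinct may also be judged with allocation known.

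At stake is the strength of the label. The selected symptoms are the ones carried forward most prominently to clinical verification, with a stated high probability for which the protocol gives no basis.

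**Working it through.** **Plan's own figures.** The protocol states no error rate for the rule, so there is none to reproduce. The prover numbers can be checked. Section 9.3 gives a minimum of 30 with 30% control, hence 21 verum and 9 control. Allowing 20% dropout, 30 / (1 - 0.20) = 37.5, or 38, against the stated 40. Section 9.4.13 gives at least 3 batches, and section 9.4.9 makes one batch placebo in the verum group. With 3 batches there are 21 × 2 = 42 IPS batches and 21 × 1 + 9 × 3 = 48 placebo batches.

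Everything below assumes an inert substance. The background rates are assumptions, because the protocol gives none.

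**Step 1: what the 13.4 exclusion does.** Let a given symptom description occur with probability p per batch, independently, with the same matching standard in both steps. A verum prover reports it on IPS with probability 1 - (1 - p)². The two-volunteer criterion is met with probability P(X ≥ 2), X binomial with n = 21. The symptom escapes 13.4 with probability (1 - p)^48. The last column is 1 - (1 - product)^50, for 50 possible descriptions.

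| p per batch | Criterion met | Escapes 13.4 | Product | At least one per trial, 50 descriptions |
|---|---|---|---|---|
| 0.5% | 1.84% | 78.6% | 1.45% | 52% |
| 1% | 6.5% | 61.7% | 4.0% | 87% |
| 2% | 20.1% | 37.9% | 7.6% | 98% |
| 5% | 62.1% | 8.5% | 5.3% | 93% |
| 10% | 92.9% | 0.6% | 0.6% | 26% |
| 20% | 99.9% | <0.1% | <0.1% | 0.1% |

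The exclusion is strong for common symptoms and weak for rare ones.

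**Step 2: any one of eight, among symptoms that survived 13.4.** Let each criterion be met by chance with probability q, independently. A symptom passes with probability 1 - (1 - q)^8. With M survivors, at least one passes with probability 1 - (1 - q)^(8M).

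| q | Symptom passes | M = 5 | M = 10 | M = 20 |
|---|---|---|---|---|
| 1% | 8% | 33% | 55% | 80% |
| 2% | 15% | 55% | 80% | 96% |
| 5% | 34% | 87% | 98% | nearly 100% |
| 10% | 57% | 98% | nearly 100% | nearly 100% |

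For example, at q = 2% and M = 10, 1 - 0.98^80 = 0.80. Because M counts survivors, these figures already allow for 13.4.

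**Step 3: the four criteria that one prover can meet.** At q = 5%, 1 - 0.95^4 = 18.5% of survivors pass, and at least one does in 64%, 87% or 98% of trials with 5, 10 or 20 survivors.

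**Step 4: how far overlap could lower this.** If all eight criteria overlapped completely, the pass rate would be q itself. At least one symptom would then pass in 10%, 18% or 33% of trials at q = 2%, and in 23%, 40% or 64% at q = 5%, for 5, 10 or 20 survivors.

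**The case against.** **Placebo is not absent.** Section 13.4 removes exact matches against both the control arm and the verum group's own placebo batch. Section 13.2 excludes symptoms in line with the prover's history or with a clear external cause, and the run-in diary gives a baseline. All of this stands, and it limits the size of the problem. It does not put a comparison into the rule.

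**A tempting stronger reading is that an inert substance passes almost every time.** A reader could get there from the two-volunteer criterion alone: for symptoms with a frequency of 8% to 20% per prover, two or more of 21 verum provers report them with probability 0.51 to 0.94. Those figures leave out 13.4. Multiplying by (1 - frequency)^24, which is the 48 placebo batches at two batches per frequency unit, gives about 7% down to 0.4%. Near-certainty also does not hold for each single symptom. It appears only at trial level, with enough survivors.

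**The list is offered as an example from a cited guideline, and its output is meant for later verification.** Other symptoms are reported under separate headings. This is true, but 14.1.1 states no other selection rule, and separate headings for the rest do not correct an unsupported label on the selected ones. A statistical analysis plan might add a comparison, but the rule and its wording are fixed in the protocol.

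**Independence is implausible.** An odd symptom and an odd modality overlap, as do the recurrence criteria. This stands, and step 4 of the working shows the lower bound.

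**Conclusion.** The concern holds in this form: the rule contains no comparison of IPS with placebo and no controlled error rate, several criteria and part of Grade I can be met from one prover, and the exact-match exclusion is weakest for the symptoms the rule favours. The stated high probability is therefore unsupported.

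How often an inert substance yields at least one attributed symptom depends on rates that the protocol does not give. With independent criteria it is 55% to 96% of trials at 2% per criterion and 87% to nearly 100% at 5%, for 5 to 20 surviving symptoms. Few survivors, low rates or strong overlap bring it well below half. A false attribution is likely over a wide range of assumptions, but it is not certain.

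**What to change.** 1. In 14.1.1 and 14.1.3, score the eight criteria and the Grade I features on every recorded symptom from IPS and placebo batches. Do this before phase 3 of section 13.3 and before the 13.4 exclusion, with one matching standard throughout.
2. After decoding, report the rate on IPS and on placebo for each criterion and for meeting at least one. Give the difference with a confidence interval that allows for repeated batches within a prover.
3. Compare recurrence across potencies only between the randomised arms, as recurrence across the same number of batches. The verum group has a single placebo batch, so a within-group comparison would favour the IPS even under no effect.
4. For individual symptoms, replace the strong wording by *candidate for clinical verification*. Make any claim of a drug effect only from the IPS-placebo comparison. One pooled interval cannot license each symptom separately, so it should not be used to restore the strong label.

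The records are already collected, so no further provers or visits are needed. The cost is some extra coding work and a weaker label. With 9 to 12 controls the intervals may be wide, which is better shown than left out.
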